## 3.4.2 Data Handling Conventions for Efficacy Analyses

For PFS, if a subject has no date of death and has not progressed by the time of the analysis, the subject will be censored at the last radiologic assessment showing that no progression has occurred.

Subjects who have no record of CR/PR and withdraw early from the trial or are lost to follow-up will be considered as non-responders for the ORR analyses and will be considered to have progression for the by-time-point PFS analyses.

## 3.4.3 Assignment of AEs to a Trial Period and Vaccination Period

Each AE will be assigned to a trial period or a vaccination period using the date of first vaccination and the date of onset of the AE.

- All AEs with onset before the date of the first trial vaccination will be classified as a baseline sign or symptom and belong to the Screening period.
- All AEs starting on or after the date of first trial vaccination will be assigned to the Treatment period and be considered TEAEs.

TEAEs will also be assigned to the following vaccination periods (See General Definitions for definitions of periods):

- Pre-radiation Vaccination Period
- Radiation Therapy Period
- Post-Radiation Vaccination Period 1
- Post-Radiation Vaccination Period 2

Per the missing data rules, missing start dates will be set to the date of first vaccination and will be considered both TEAEs and part of the Treatment period.

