**BRACHY-CHOR-001** 

Overall Treatment Period: All data collected from the first vaccination of trial treatment through the last trial visit (regardless of completion status) will be considered part of the overall treatment period. A final visit is planned for approximately 30 days after the last treatment visit. Specifically, the overall treatment period will consist of the pre-radiation vaccination period, radiation therapy period, post-radiation vaccination period 1 and post-radiation vaccination period 2, which are defined below.

**Pre-Radiation Vaccination Period**: The time from the date of first vaccination of MVA-BN-Brachyury to the day prior to the start of radiation therapy. Subjects should have received 2 doses of MVA-BN-Brachyury and 1 dose of fowlpox (FPV)-Brachyury during this period.

**BN-Brachyury:** Term that refers to both MVA-BN-Brachyury and FPV-Brachyury trial vaccines when used together in a prime-boost regimen.

**Radiation Therapy Period**: from the start date of radiation therapy to the day prior to resuming FPV-Brachyury injections.

**Post-Radiation Vaccination Period 1**: The time from the date of restart of FPV-Brachyury injections after radiation therapy to the day prior to the scheduled FPV-Brachyury injection at the End Radiation + 26 weeks visit. FPV-Brachyury will be administered every 4 weeks during this period.

**Post-Radiation Vaccination Period 2**: The time from the date of the FPV-Brachyury injection at the End Radiation + 26 weeks visit to the last scheduled trial visit (i.e., last injection of FPV-Brachyury + approximately 30 days). FPV-Brachyury will be administered every 12 weeks during this period.

**Treatment Emergent Adverse Events**: An AE with an onset on or after initiation of trial treatment, or an AE present at initiation of trial treatment that worsens (*i.e.*, increase in severity: On-Trial Grade > Baseline Grade) as determined by the investigator will be considered a treatment-emergent adverse event (TEAE). TEAEs are collected through the last scheduled visit (approximately 30 days after the last dose of trial product).

Serious Adverse Events (SAEs) and AEs of Special Interest (AESIs): SAEs and AESIs that occur on or after initiation of trial treatment through 30 days after the last dose of trial product are considered as TEAEs. SAEs and AESIs will be followed until resolution.

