#### 3.5.8.2 Adverse Events

All AEs observed by the investigator and/or reported by the subject will be recorded in the eCRF regardless of the assessment of relationship to the trial treatment. Verbatim descriptions of AEs will be mapped to MedDRA version 21.0 (or higher) and graded for severity per NCI-CTCAE, Version 4.0 or higher.

A TEAE is an adverse event that presents itself during or following initiation of trial treatment or worsens in severity after the initiation of trial treatment (Refer to General Definitions for details). The algorithm for the assignment of AEs as treatment emergent in the case of missing data can be found in Section 3.4.1. Non-TEAEs, including baseline signs and symptoms, will not be included in the table summary but will be flagged in the subject-level listings. TEAEs will be further assigned to the following treatment periods: Pre-radiation Vaccination Period, Radiation Therapy Period, Post-Radiation Vaccination Period 1 and Post-Radiation Vaccination Period 2.

All TEAEs will be summarized overall and by treatment periods, SOC, and PT, sorted by descending frequency. For each specific TEAE a subject will be counted only once within an SOC and PT. Also, two separate tables will summarize TEAEs by treatment period (including the overall treatment period), with the first table summarized further by PT sorted by descending frequency of PT, and the second table summarized further by SOC and High-Level Term (HLT), sorted by descending frequency of HLT. Similar summaries will be provided for all Grade 3 or above TEAEs, related TEAEs, Grade 3 or above related TEAEs, SAEs, related SAEs, AEs that lead to discontinuation of any trial product (MVA-BN-Brachyury, FPV-Brachyury, and Radiation), TEAEs leading to death, and non-serious TEAEs occurring at a frequency ≥5% any treatment group.

A separate table will summarize AEs related to MVA-BN-Brachyury or FPV-Brachyury, and AEs related to radiation therapy for the overall treatment period by SOC and PT.

Additional summaries by severity based on NCI-CTCAE grade in which a subject is presented at the maximum severity within the SOC, and PT categories will also be generated. Similarly, summaries based on causality will be created where a subject is counted at their maximum causality for each SOC and PT experienced. These additional summaries will be presented for the overall treatment period and sorted by descending frequency of SOC and PT (regardless severity or causality level).

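### SAP 3.4.3 assigns adverse events by onset date alone, which contradicts the TEAE definition for pre-existing events that worsen and leaves those events without a treatment period

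*SAP*

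**What the plan says.** SAP 3.4.3 assigns each AE to a period "using the date of first vaccination and the date of onset of the AE". It has two main branches. The first reads: "All AEs with onset before the date of the first trial vaccination will be classified as a baseline sign or symptom", and it places these events in the Screening period. For the rest: "All AEs starting on or after the date of first trial vaccination will be assigned to the Treatment period and be considered TEAEs". The only addition is that an event with a missing start date is treated as starting on the day of first vaccination.

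The definition of a TEAE is wider. SAP General Definitions covers events that begin on or after the start of treatment, "or an AE present at initiation of trial treatment that worsens", judged by whether the on-trial grade exceeds the baseline grade. SAP 3.5.8.2, which specifies the AE tables, repeats that an event is treatment-emergent if it "worsens in severity after the initiation of trial treatment" and refers back to General Definitions. Protocol 10.4.6 has the same worsening limb.

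On presentation, SAP 3.5.8.2 says: "Non-TEAEs, including baseline signs and symptoms, will not be included in the table summary but will be flagged in the subject-level listings". SAP Section 4, which lists changes from the planned analyses, mentions no change to the TEAE definition.

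**The concern.** The assignment rule and the definition disagree about an event that is already present at first vaccination and then worsens. Section 3.4.3 is the rule a programmer would apply to each record, and neither grade nor date of worsening is an input to it. Followed literally, together with the exclusion in 3.5.8.2, it keeps such an event out of the TEAE summaries, including Grade 3 or above.

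Confirming the safety profile is a secondary objective, and any error runs towards under-reporting. That is out of step with the rest of the SAP. Section 3.4.1 moves an ambiguous start date to the day of first vaccination, and 3.4.4.2 treats missing causality as related.

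**Working it through.** The plan states no figure on this point and no arithmetic applies. The check sets the rules side by side and follows one event through them.

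**Test case (illustrative).** An AE begins after consent and before first vaccination at Grade 1. It rises to Grade 3 during the radiation therapy period.

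| Rule applied | Classification | In TEAE and Grade 3+ tables? | Treatment period |
|---|---|---|---|
| SAP 3.4.3, literal | Screening, baseline sign or symptom | No, listing only | None |
| SAP General Definitions, SAP 3.5.8.2, Protocol 10.4.6 | TEAE by worsening | Yes | Not defined |
| Either rule, if the site opens a new AE dated at the worsening | TEAE by onset | Yes | Radiation therapy period |

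**Step 1: is there a conflict?** Yes. The first two rows give opposite answers for one record, and nothing in the SAP says which prevails.

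**Step 2: does the definition alone repair it?** No. 3.5.8.2 tabulates TEAEs by four periods: pre-radiation vaccination, radiation therapy, and post-radiation vaccination 1 and 2. The earliest of these starts on the day of first vaccination. An event that began before that day falls in none of them when onset is the only date used.

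**Step 3: do the recording rules settle it?** Not fully. Protocol 8.1.1 counts the worsening of an existing condition as an AE, which supports the third row. Neither document says that an AE already open must be closed and re-entered with a new onset date. The definition's own test compares two grades of one event. If every worsening became a new record with post-vaccination onset, that limb would be redundant.

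**Step 4: which events are exposed?** Protocol 9.5.1 starts AE collection at consent, and Protocol 9.1 places earlier conditions in medical history. SAP 3.5.8.1 has findings after consent entered on the AE form as baseline signs and symptoms, and the screening assessments include a complete neurologic examination. The exposed set is therefore mainly events and findings recorded between consent and first vaccination. The procedure schedule wants history, examination and laboratory work within 16 days of starting treatment, and baseline imaging within 28 days, so this window is probably short.

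**The case against.** The strongest reply is that three separate statements, one of them in the section that builds the tables, already include worsened events. The exclusion in 3.5.8.2 applies to non-TEAEs, and under the definition in that same paragraph a worsened event is a TEAE. On this view 3.4.3 is loose drafting that a careful programmer would read in the light of the definition. In addition, Protocol 8.1.1 makes a worsening an AE, and SAP 3.5.8.1 has findings discovered after treatment starts reported as AEs. A new record dated at the worsening would be handled correctly by 3.4.3 as it stands. There are also partial safeguards: laboratory shifts to worst grade by period, BPI-SF shift tables by period, and subject-level listings of all AEs.

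Much of this stands. It shows that omission is a risk and not a settled outcome, and it narrows the affected set. It does not reconcile the two rules, and it does not supply a period for a worsened event. The new-record practice is plausible, but no rule in the documents requires it. The shift tables cover laboratory values and pain scores, not clinical AEs in general.

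A reader might go further and infer that the tables will hide the worsening of long-standing chordoma pain and neurologic deficits. The documents do not support that. Conditions that predate consent belong to medical history, and their worsening may enter as a new AE with onset on treatment.

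**Conclusion.** SAP 3.4.3 is wrong as written. It contradicts the TEAE definition in the SAP and the protocol, and it leaves a worsened pre-existing event without a treatment period even if the definition is followed.

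An undercount of TEAEs and Grade 3 or above TEAEs follows only if two conditions hold: 3.4.3 is programmed literally, and the worsening is not entered as a separate AE. The missing period matters whenever the worsening stays on the original record.

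The size cannot be given. A reader might be tempted to express it in percentage points on 29 patients. The documents give no frequency of such events, and the safety denominator is the FAS (all dosed patients), which can exceed 29 because non-evaluable patients may be replaced. Affected events would still appear in the listings.

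**What to change.** Amend SAP 3.4.3 along these lines: an AE that began before first vaccination, and whose grade rises above its baseline grade on or after first vaccination, is a TEAE. It is assigned to the period containing the date of worsening and tabulated at the post-worsening grade. This brings 3.4.3 into line with the SAP's and the protocol's own definition.

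Also state that the worsening is recorded in the eCRF with its own date and grade, for example as a new AE record. This second part is needed because the documents do not show that one AE record holds both a baseline and a later grade with a date of change. Without those data the amended rule cannot be programmed.

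The cost is one sentence in the SAP, a derivation check and possibly an eCRF completion instruction. Any worsening already held on a single record would need its date and grade confirmed by query.

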## **9.5 Reporting**

### **9.5.1 Collecting and Recording Adverse Events**

The Investigator will monitor the occurrence of adverse events for each patient during the course of the trial. All AEs (as defined above) reported by the patient, observed by the Investigator, or documented in medical records will be listed on the AE-section of the eCRF, whether believed by the Investigator to be related or unrelated to the trial vaccine.

All AEs must be reviewed, graded and causality determined by an Investigator listed on the form FDA 1572 at the research center reporting the event(s). Collection of adverse events begins at the time the patient signs informed consent and continues until the final Post-Treatment Follow-up Visit.

Adverse event terms should be recorded concisely, using acceptable medical terms. When possible, a diagnosis (i.e., disease or syndrome) rather than the component signs and symptoms

should be recorded on the eCRF (e.g., congestive heart failure rather than dyspnea, rales, and cyanosis). However, signs and symptoms considered unrelated to syndromes or diseases are to be recorded as individual adverse events on the eCRF (e.g., if congestive heart failure and severe headache are observed at the same time, each event is to be recorded as an individual adverse event). Only abnormal laboratory values that result in clinical sequelae or require medication for treatment should be recorded as an adverse event. The adverse event should not be recorded as a procedure or clinical measurement (i.e., a laboratory or vital sign). The underlying reason for the procedure or the abnormal clinical measurements, and, whenever possible, a diagnosis, should be recorded. The diagnosis should be recorded; not the individual lab test name.

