## 3.4 Data Conventions and Handling of Missing Data

## 3.4.1 Missing or Partial Dates

All data will be listed as captured in the electronic case report form (eCRF); however, it may be necessary to impute incomplete dates to correctly assign events to a period or to calculate durations.

For prior and concomitant medications, AEs, and cancer history dates, the following rules will apply:

BRACHY-CHOR-001

BN-Brachyury-TRICOM Vaccine

02 November, 2021

Missing	Rule for Start Date	Rule for End Date	Imputation Flag			
Day	First of Month	Last of Month	D			
Month	01 January	31 December	M			
Year	First Treatment Date	Date of Data Cutoff/Lock	Y			

If the imputation of an AE start date leads to a date prior to the date of first vaccination, and it is possible that the AE start date can be on or after date of first vaccination based on partial date information (e.g., occurred on the same month), it will be set to the date of first vaccination to be conservative. In the event the imputation of an end date leads to a date after the death date of a subject, the death date will replace the imputed date.

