
AESIs are flagged on the general AE eCRF page, with additional information on the event of interest collected on an additional AESI/SAE-specific page. AESIs will be summarized overall and by treatment period and by SOC and PT sorted by descending frequency.

Injection site reaction AEs will be summarized by selecting AEs that have injection site reactions indicated as the AE high level term. Summary tables will be created overall and by treatment period, and by PT sorted by descending frequency.

BRACHY-CHOR-001

Additionally, an immunotherapy toxicity table will be created by PT. It will include frequency summaries for treatment delay, treatment discontinuation, required hospitalization, death, complete resolution, incomplete resolution, high-dose steroids use and use of additional immune-suppressing agents. Summary statistics (median, minimum and maximum) will also be included for trial day of onset of the event and trial day of event resolution (Tsimberidou et al., 2018). All AEs will be included in the subject-level listings. Separate listings of SAEs, AESIs, AEs leading to death and AEs leading to discontinuation of any trial treatment will also be presented.

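### AE start-date imputation ignores a known end date, so an adverse event that ended before first vaccination can be counted as treatment-emergent

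*SAP*

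**What the plan says.** SAP 3.4.1 gives the purpose of imputation: "it may be necessary to impute incomplete dates to correctly assign events to a period or to calculate durations". For an adverse event (AE) start date:

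- A missing day becomes "First of Month".
- A missing month becomes 1 January.
- A missing year becomes "First Treatment Date".

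There is one override for AE starts. It opens "If the imputation of an AE start date leads to a date prior to the date of first vaccination, and it is possible" on the partial information that onset came on or after first vaccination, and it then uses the first-vaccination date. For end dates, a missing day becomes the last of the month, a missing month 31 December, and a missing year the data cutoff or lock. The only check on an imputed end date is a cap at death.

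SAP 3.4.3 classifies an AE with onset before first vaccination as a baseline sign or symptom in the Screening period. It then adds that "missing start dates will be set to the date of first vaccination and will be considered both TEAEs and part of the Treatment period". SAP 3.5.8.2 refers back to 3.4.1 for missing dates and adds no rule. Protocol 9.5.1 makes pre-dose AEs part of the data: "Collection of adverse events begins at the time the patient signs informed consent".

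**The concern.** An event that is known to have ended before first vaccination must have begun before it. By the SAP's own Screening rule it is a baseline sign or symptom. The imputation rules never consult the end date, so they can reclassify such an event as a TEAE and create a record whose start follows its end. That defeats both stated purposes of imputation, since the period is wrong and the duration is negative.

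Confirming the safety profile of the combination is a secondary objective, and the TEAE tables are its main evidence. A similar gap exists for end dates. SAP 3.5.8.2 plans an immunotherapy toxicity table in which "Summary statistics (median, minimum and maximum) will also be included for trial day of onset of the event and trial day of event resolution", and an end date imputed to the data cutoff could enter it.

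**Working it through.** The plan states no figure on this point to reproduce, so the rules are applied as written.

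**1. Worked records, first vaccination on 20 March.** Duration is end - start + 1.

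| Recorded start | Recorded end | Table value | Final start | Duration | Class under the SAP |
|---|---|---|---|---|---|
| Missing | 10 March | 20 March | 20 March | 10 - 20 + 1 = -9 days | TEAE (wrong) |
| March, day unknown | 10 March | 1 March | 20 March (override) | -9 days | TEAE (wrong) |
| March, day unknown | 25 March | 1 March | 20 March (override) | 25 - 20 + 1 = 6 days | TEAE (reasonable, as onset is ambiguous) |
| February, day unknown | 10 March | 1 February | 1 February | positive | Screening (right) |

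**2. Where the fault lies.** A start imputed to the first of the month or to 1 January is never later than the true onset, so it cannot fall after the end. Only the first-vaccination date can. The imputed start exceeds a known end only when the start was set to first vaccination and the end precedes it.

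**3. How readily this case triggers.** With a wholly missing start it always does. With only the day missing, the override applies when true onset and first vaccination share a calendar month. For an onset k days before first vaccination, with first vaccination equally likely on any day of the year, the share is (365 - 12k)/365. Averaged over k = 1 to 16 (the screening window in Protocol 4.2.1, uniform lag assumed), it is 1 - 12 x 8.5/365 = 1 - 102/365 = 72.1%. This is conditional on the day being missing.

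**4. Size of one false TEAE.** 1/29 = 3.4 percentage points for its preferred term. The 29 is the evaluable target. Safety uses the Full Analysis Set of everyone dosed, including replaced subjects, so at full accrual 3.4 is an upper figure.

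**5. End dates.** An end date with missing year goes to the cutoff or lock unless the subject died earlier. The last visit is not consulted. Within a preferred term, one such value is the median if it is the only event, pulls the median if there are two, and tends to set the maximum.

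**6. Later period boundaries.** The Pre-Radiation Vaccination Period is "The time from the date of first vaccination of MVA-BN-Brachyury to the day prior to the start of radiation therapy". No imputation rule refers to radiation start, FPV restart or the End Radiation + 26 weeks injection. If radiation starts on 8 May, an AE recorded as May with true onset on the 20th is dated 1 May and falls in the vaccine period.

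Take boundary day b and onset day o as uniform over a 30-day month (an assumption):

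- First-of-month rule: wrong when b > 1 and o >= b. The count is 29 + 28 + ... + 1 = 435, and 435/900 = 48%, all towards the earlier period.
- Set-to-boundary rule: wrong when b > 1 and o < b. The count is 1 + 2 + ... + 29 = 435, again 48%, all towards the later period.

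Over whole periods, missing-day events moved to an earlier period are about 75%, 57% and 20% of Radiation Therapy Period events for courses of 1, 12 and 59 days. The figures are about 9% in Post-Radiation Period 1 and 2% in Period 2. These assume uniform onset within each period and FPV resuming two weeks after radiation. Wholly missing starts send every radiation and booster event to the first period.

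**The case against.** The strongest reply is that the case is rare and errs on the safe side. Conditions before consent are medical history (Protocol 9.1), and screening is short, generally 16 days. A post-consent event with an unknown start but a known pre-dose end should be uncommon. eCRFs are due within 5 days of each visit and the data are queried. Initial SAE reports must carry an onset date, and AESIs follow the same process. Original values are listed as captured and imputations are flagged, so affected records can be found. Overcounting TEAEs is conservative against first dose, which is the SAP's stated intent. It could also be argued that the reference to partial date information already lets the end date be used.

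Most of this stands as a limit on size. It does not rescue the rule. The text does not say that the end date counts as partial information, and the rule for wholly missing starts has no condition at all. Conservatism is a reason to resolve doubt towards TEAE status, but an event that ended before dosing leaves no doubt to resolve.

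On end dates, the table is a single descriptive one, and the SAP does not say that imputed ends feed it. It does not exclude them either.

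**Conclusion.** The defect is real and narrow. As written, the rules turn a screening AE with a known pre-dose end into a TEAE with a start after its end, contrary to the Screening rule in the same section. The effect is limited to AEs with incomplete dates, whose rate the documents do not give. The primary ORR analysis is untouched. The missing last-contact cap on end dates is a lesser gap.

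A reader might infer three stronger points that the documents do not support.

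- **That the shift at later boundaries is an error with a ready correction.** The shift runs only to earlier periods, but setting dates to the boundary reverses it at the same 48% on the same assumption. It also leaves open which boundary applies when several are possible. This is a choice of convention. Causality is recorded for each product, and the overall-period tables by product relatedness do not depend on it.
- **That all of these rules produce impossible records.** Only the start-after-end case does. A date of the 1st in a boundary month is possible.
- **That resolution times are inflated by months or years.** The documents give neither a data cutoff date nor last-visit dates, so the size cannot be stated.

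**What to change.** In SAP 3.4.1 and 3.4.3, add:

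1. An imputed AE start date may not be later than the known end date or, for a partial end date, the latest date it allows.
2. An AE whose end date, judged the same way, is before first vaccination stays in Screening as a baseline sign or symptom, whatever is missing from its start date.
3. Secondary: an imputed AE end date is capped at the subject's last trial contact, including SAE and AESI follow-up, as well as at death. End dates with an imputed year are left out of the resolution-day summary.

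With items 1 and 2, start-after-end records of this kind, and TEAEs known to have ended before dosing, fall to zero. Events whose end date leaves onset ambiguous keep the present conservative treatment. No change to the later period boundaries is part of this fix.

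The cost is a few sentences in the SAP and a small edit to the AE derivation program. No new data are needed.
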